### **2) IRB Review History\***

N/A

### **3) Objectives\***

This is a 24-week, randomized, double-blind, placebo-controlled trial of exenatide weekly injection (2mg per dose) as an adjunctive therapy in 70 schizophrenia subjects to examine exenatide's effects on negative symptoms and cognition.

Primary aim: Examine the efficacy of exenatide weekly injection in improving negative symptoms as measured by the Scale for the Assessment of Negative Symptoms (SANS) total score.

Secondary aims: Examine the efficacy of exenatide in improving cognition as measured by the MATRICS Consensus Cognitive Battery (MCCB) composite score.

Tertiary/exploratory aims:

1. Examine exenatide's effect on schizophrenia symptoms as measured by the Positive and Negative Syndrome Scale (PANSS) total score.
2. Examine the efficacy of exenatide in improving social function as measured by the Instrumental Activities of Daily Living Scale (IADL) and the Heinrichs Carpenter Quality of Life Scale (QLS).
3. Examine exenatide's effect on neuro-protection as measured by the change in hippocampal volume.
4. Examine exenatide's effects on inflammatory markers including serum levels of high sensitivity CRP, IL-6, and TNF- $\alpha$ .
5. Examine the potential moderator role of baseline serum levels of CRP, IL-6, TNF- $\alpha$ , and baseline hippocampal volume for exenatide's effects on negative and cognitive symptoms.
6. Examine the potential mediator role of changes from baseline in serum levels of CRP, IL-6, TNF- $\alpha$ , and hippocampal volume for exenatide's effects on negative and cognitive symptoms.
7. Examine the efficacy of exenatide in reducing body weight and improving glucose metabolism as measured by fasting plasma glucose and HbA1c.
8. Examine the safety and tolerability of exenatide as measured by changes in the side effects questionnaire (SEQ, SEQabbrev), EKG and vital signs

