### **Exclusion Criteria:**

- 1) inability to provide informed consent, or for individuals with a legal guardian, inability to provide assent or a lack of informed consent from the legal guardian
- 2) current substance abuse
- 3) Subjects who are not on a stable dose of an antipsychotic medication for at least a month prior to enrollment
- 4) psychiatrically unstable per treating clinician's judgment
- 5) Uncontrolled medical condition including uncontrolled hypertension, diabetes, seizure disorder, severe cardiovascular, cerebrovascular, pulmonary, thyroid diseases, and gastroparesis.
- 6) history of ketoacidosis
- 7) currently taking insulin
- 8) currently taking meglitinides (repaglinide and nateglinide)

- 9) currently on immunosuppressant medication regularly including oral steroids; topical and inhalant steroids are allowed
- 10) currently on sulfonylurea drugs (e.g. glyburide)
- 11) Current, active chronic infection (including tuberculosis, HIV and hepatitis), malignancy, organ transplantation, blood dyscrasia, central nervous system demyelinating disorder, and any other known autoimmune or inflammatory condition
- 12) pregnant or breastfeeding.
- 13) prisoners
- 14) Exclusionary labs: eGFR < 35 ml/min

Hematology (CBC)	
Leukocytes	<2 or $>17.5 \times 10^3/\text{mm}^3$
Platelets	<75 or $>700 \times 10^3/\text{mm}^3$
Comprehensive Metabolic Panel	
Sodium	<1.1 times the lower limit ( $\leq 121.5$ ) or $>1.1$ times upper limit ( $\geq 159.5$ ) of the reference range
Potassium	<1.1 times the lower limit ( $\leq 3.15$ ) or $>1.1$ times upper limit ( $\geq 5.83$ ) of the reference range
Glucose	$>2$ times the upper limit ( $>198$ ) of the reference range
Blood Urea Nitrogen (BUN)	$>1.3$ times upper limit ( $>29.9$ ) of the reference range
Creatinine	$>1.3$ times upper limit ( $>1.69$ ) of the reference range
Total bilirubin	$>2$ times the upper limit ( $>2.4$ ) of the reference range
Aspartate amino transferase (AST)	$>3$ times upper limit ( $>120$ ) of the reference range
Alanine amino transferase (ALT)	$>3$ times upper limit ( $>120$ ) of the reference range
Alkaline phosphatase (ALP)	$>3$ times upper limit ( $>345$ ) of the reference range
Hemoglobin A1C	Patients with a value $\geq 9.0\%$

All exclusionary labs will be reviewed prior to administration of the study drug.

We will continue our recruitment efforts to assure a meaningful representation of women and minority populations.

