### Safety Endpoints:

An EKG will be conducted at the beginning and end of the study to assess safety. Vital Signs including blood pressure will be collected at every visit. Data on adverse events will be collected at every visit using the side effects questionnaires (SEQ and SEQabbrev) to assess safety and tolerability.

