Continuous data and safety monitoring will be conducted by the PI. The monitoring will include all adverse events (AEs and SAEs) both expected and unexpected, enrollment, dropout rates and protocol deviations in addition to the results of special studies and laboratory tests that are conducted to ensure patient safety, subject interview and conduct, review of subject symptom or performance status, review of clinical test results, review of subject physical examination, review of all vital signs, diagnostic tests, and evaluations. The investigator will report adverse events to the IRB in accordance with IRB guidelines.

The PI will create a Data Safety Monitoring Board (DSMB) to independently oversee this clinical trial. The DSMB for this study will be composed of at least three people and will include a psychiatrist, an endocrinologist and a biostatistician who will be independent of the study group. The group will follow the NIH policy for data and safety monitoring and guidelines as published on <http://www.nimh.nih.gov/research-funding/grants/nimh-policy-on-data-and-safety-monitoring-in-extramural-investigator-initiated-clinical-trials.shtml>. Study data regarding subject enrollment, characteristics, symptoms, adverse events and serious adverse events will be submitted to the DSMB for review and analysis annually. The DSMB will review study data, the safety of study participants and conduct of the study. It will advise the PI on continuation of the study and provide reports to the IRB regarding recruitment of appropriate subjects and presence of adverse effects.

An explicit stopping rule will be followed for a potentially serious psychiatric decompensation in order to further enhance patient safety: active subjects will be terminated from the study if they experience an increase in PANSS total score greater than or equal to 20 compared to their baseline score at any point during the study.

Subjects will be terminated from the study if their eGFR falls below 30 ml/min at any point during the study.

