#### **14) Withdrawal of Subjects\***

Subjects will be withdrawn from the study if they are determined to meet ineligibility criteria after enrollment. If subjects have laboratory results that meet the exclusionary criteria range during the study, the subject will have his/her labs repeated before being withdrawn from the study.

The study medication will be stopped if a subject has a serious adverse event, but will not necessarily be stopped for exacerbation of psychiatric symptoms or any other adverse event. If the PI or co-investigator considers continuation of the study medication to be safe after a worsening of psychiatric symptoms, and the subject wishes to continue, the subject's treating psychiatrist will be contacted and will make the final decision whether the subject will be allowed to continue taking study medication.

Female subjects may be terminated from the study if they become pregnant at any time while participating in the study. Subjects who fail the urine screening for illegal drugs during the screening visit will be deemed a screen fail and terminated from the study. We will not document the results from the urine drug screen in the patient study records. We will maintain a separate log of the reasons for screen fail. This log will have the counts of screen fails for various exclusion factors including current substance abuse. This log will have no subject information and will have no link to subject id.

Subjects may also withdraw their consent from the study at any time for any reason, including: physical or emotional discomfort associated with taking the study medication, physical or emotional discomfort associated with performing study procedures, or inability to come in for required study visits.

If at any time the study sponsor or research personnel at UMass decide to terminate the study, subjects' consent will be withdrawn involuntarily.

For subjects terminated or withdrawn from the study, they will be asked to have an "exit" visit. Vital signs, ECG, side effect assessment and routine blood tests (CBC, basic metabolic profile) will be performed during the visit.

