#### 2) Acute Pancreatitis.

Based on postmarketing data, exenatide has been associated with acute pancreatitis, including fatal and non-fatal hemorrhagic or necrotizing pancreatitis.

3) Hypoglycemia

The endocrine responses of exenatide treatment are glucose dependent. Exenatide by itself usually does not cause hypoglycemia. Hypoglycemia may occur if it is prescribed with other anti-diabetic medications such as sulfonylurea. Therefore, patients who are currently on sulfonylurea are excluded from the study.

4) Kidney Problems

There have been postmarketing reports of altered renal function with exenatide, including increased serum creatinine, renal impairment, worsened chronic renal failure and acute renal failure, sometimes requiring hemodialysis or kidney transplantation. Some of these events occurred in patients receiving one or more pharmacologic agents known to affect renal function or hydration status such as angiotensin converting enzyme inhibitors, nonsteroidal anti-inflammatory drugs, or diuretics. Some events occurred in patients who had been experiencing nausea, vomiting, or diarrhea, with or without dehydration. Reversibility of altered renal function has been observed in many cases with supportive treatment and discontinuation of potentially causative agents, including exenatide. Exenatide has not been found to be directly nephrotoxic in preclinical or clinical studies.

5) Allergic Reaction

There have been postmarketing reports of serious hypersensitivity reactions (e.g. anaphylaxis and angioedema) in patients treated with exenatide.

6) Common Side effects

The most common side effects of exenatide include nausea, diarrhea, headache, vomiting, constipation, itching at the injection site, small bump at the injection site and indigestion.

Common	Less Common	Rare
Nausea, vomiting, diarrhea, injection site nodule, constipation, headache	dyspepsia	Pain in the stomach area (abdomen)
	Low blood sugar (shakiness, confusion, feeling jittery, weakness, drowsiness and dizziness, hunger,	Shortness of breath, swelling of eyes, face, tongue, lips, throat,

	irritability and fast heartbeat)	arms, hands, feet, ankles or lower legs.  Lump or swelling in the neck, hoarseness, trouble breathing or swallowing,
--	----------------------------------	--

**Risk of EKG testing:** There are also small risks in using EKG equipment, such as skin irritation. However, all research members involved in EKG testing have experience in operating the machinery.

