Baseline visit: Eligible subjects came to the clinic for the baseline visit. Fasting blood samples for glucose, insulin, HbA1c, lipid profile, comprehensive metabolic profile, CBC, high sensitivity C-reactive protein (hsCRP), and tumor necrosis factor α (TNF- α) were obtained. The subject completed the clinical symptoms assessment, the extrapyramidal symptoms (EPS) assessment, and vital signs. Then the subject received the study medication (either exenatide 2mg or placebo weekly injection). The randomization was based on a double-blinded 1:1 ratio using permuted block with randomly varying block size.

Follow-up visits (week 1-24): Subjects came to the clinic weekly to receive the study medication injection; possible side effects were assessed weekly. At week 6, 12, 18, 24 visits, vital signs, the clinical symptoms assessment and the EPS assessment were repeated; fasting blood samples for glucose, insulin, HbA1c, lipid profile, comprehensive metabolic profile, CBC, hsCRP, and TNF- α were obtained.

Clinical symptoms assessment: The clinical symptoms assessment included: The Scale for Assessment of Negative Symptoms (SANS), the Positive and Negative Syndrome Scale (PANSS), the Clinical Global Impression Scale (CGI), the Calgary Depression Scale for Schizophrenia (CDSS), the Heinrichs Carpenter Quality of Life Scale (QLS), the Instrumental

Activities of Daily Living Scale (IADL), and the MATRICS Consensus Cognitive Battery (MCCB).

EPS assessment: The EPS scales included: the Simpson-Angus Scale, the Barnes Akathisia Scale, and the Abnormal Involuntary Movement Scale (AIMS).

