Statistical analysis: Statistical analysis was performed using SPSS (version 24.0, IBM Corp, Armonk, NY, USA). Descriptive statistics were performed to summarize demographic and clinical characteristics of the study sample. Group comparisons were performed using independent samples t test for continuous variables and the Fisher exact test or Chi-square test for categorical variables. The outcome measures were repeated at different time points. Therefore, analysis of repeated measures using mixed models was performed to compare the change over time in outcome measures between the two treatment groups while controlling for potential confounding variables. The mixed model approach does not require subjects to have the same number of study visits or measurements and uses all available data instead of eliminating subjects with missing data, resulting in unbiased estimates of the model parameters when data are missing at random. Further, for those who completed 24-week treatment, analysis of covariance (ANCOVA) was used to compare change scores from baseline to week 24 between the two treatment groups controlling for potential confounding variables. For all analyses, a P value less than 0.05 (two-tailed) was used for statistical significance.

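### eGFR is measured serially for a named renal risk, but no safety endpoint or SAP analysis compares it between arms

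*Protocol*

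**What the plan says.** **Renal risk and its handling (protocol).** Section 15, under Kidney Problems, states: "There have been postmarketing reports of altered renal function with exenatide". It goes on to mention acute renal failure, sometimes needing dialysis or transplantation. Section 10 draws eGFR at screening and at weeks 6, 12, 18 and 24. Three passages attach a rule to it:

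- Section 5: "Exclusionary labs: eGFR < 35 ml/min".
- Section 13: "Subjects will be terminated from the study if their eGFR falls below 30 ml/min at any point during the study".
- Section 14: "If subjects have laboratory results that meet the exclusionary criteria range during the study, the subject will have his/her labs repeated before being withdrawn".

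**Safety measures (protocol).** Exploratory aim 8 in Section 3 is: "Examine the safety and tolerability of exenatide as measured by changes in the side effects questionnaire (SEQ, SEQabbrev), EKG and vital signs". Section 9 lists EKG and vital signs as safety endpoints, then adds: "Data on adverse events will be collected at every visit using the side effects questionnaires (SEQ and SEQabbrev) to assess safety and tolerability". Neither place names a laboratory value.

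**SAP.** eGFR appears once, as an exclusion criterion under Participants. The follow-up laboratory list under Procedures is "fasting blood samples for glucose, insulin, HbA1c, lipid profile, comprehensive metabolic profile, CBC, hsCRP" and TNF-α; the Bioassay paragraph also leaves eGFR out. The statistical analysis paragraph gives descriptive statistics, t tests, Fisher or chi-square tests, a mixed model for change over time in outcome measures that it does not name, and then: "for those who completed 24-week treatment, analysis of covariance (ANCOVA) was used to compare change scores from baseline to week 24". It ties none of these to adverse events, laboratory safety or renal function.

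**The concern.** The protocol treats renal function as a safety matter in eligibility, in the visit schedule and in the removal rules, but not in the analysis. The report could therefore give a safety conclusion for exenatide in schizophrenia with no renal comparison by arm, although the values were collected.

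The methods the SAP gives for change in outcome measures would also serve this harm poorly if they alone were applied to eGFR. The expected pattern is a large fall in a few subjects. A comparison of means spreads those falls over the whole arm, and a completer analysis leaves out the subjects whom the eGFR rules remove.

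**Working it through.** **The plan's own figure.** The only sample-size statement (protocol Section 12) concerns efficacy: 60 evaluable subjects, effect size 0.74, two-tailed alpha 0.05, 80% power. With 30 per arm, a two-sample noncentral t calculation gives 80.5%, so the figure reproduces. It says nothing about renal safety.

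**Inputs for the renal check.** The randomisation goal is 70 at 1:1 (Sections 6 and 10), hence 35 per arm. The documents give no renal event rate, size of fall or SD of eGFR change. Assumed: 2 or 3 affected exenatide subjects, none on placebo, a fall of 30 to 40 ml/min each, and an SD of change of 10 to 20 ml/min.

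**1. Dilution in a comparison of means.** Mean shift = k × fall / 35. SE = SD × √(2/35), which is 2.39, 3.59 and 4.78 for SD 10, 15 and 20. Power is two-sided noncentral t with 68 df.

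| Affected (k) | Fall, ml/min | Mean shift | Power, SD 10 | SD 15 | SD 20 |
|---|---|---|---|---|---|
| 2 | 30 | 60/35 = 1.7 | 11% | 8% | 6% |
| 2 | 40 | 80/35 = 2.3 | 16% | 10% | 8% |
| 3 | 30 | 90/35 = 2.6 | 19% | 11% | 8% |
| 3 | 40 | 120/35 = 3.4 | 29% | 16% | 11% |

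These powers are generous, because the large falls also widen the spread in their own arm. Adding that variance, fall² × p(1−p) with p = k/35, to the exenatide arm and averaging the two arms' variances gives, for a 40 ml/min fall and SD 10 to 15, 12 to 9% (k = 2) and 20 to 13% (k = 3).

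For scale, the mean difference detectable with 80% power at the plan's effect size is 0.74 × SD, or 7.4 to 14.8 ml/min for SD 10 to 20. Every shift in the table is well below that.

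**2. Completer ANCOVA.** A subject removed for eGFR before week 24 has not completed treatment and contributes nothing. If all affected subjects were removed, the shift in this analysis is about zero.

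**3. What a count by arm can show (35 v 35).**

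- Fisher exact, two-sided: 2 v 0 gives p = 0.49, 3 v 0 gives 0.24, 5 v 0 gives 0.054 and 6 v 0 gives 0.025. Six against none are needed for p < 0.05.
- Exact 95% interval for 2/35 (5.7%): 0.7 to 19.2%.
- Upper two-sided 95% limit for 0/35: 1 − 0.025^(1/35) = 10.0%.
- Chance of at least one event in the exenatide arm, 1 − (1 − rate)^35: 30% at a true rate of 1%, 66% at 3%, 83% at 5%.

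A count shows every case but cannot carry a formal test at this size, so the table is descriptive.

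**4. Who counts as removed for eGFR.** Section 13 ends participation below 30 ml/min. Section 14 speaks of withdrawal, after repeat tests, for results in the exclusionary range, which Section 5 sets at below 35 ml/min. A confirmed value between 30 and 35 is covered by one rule and not the other, so the number removed for eGFR is not yet defined.

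**The case against.** The strongest reply is that renal harm is watched. Section 13 has the investigator monitor all adverse events, safety laboratory tests, dropout rates and reasons for stopping study medication; adverse events go to the IRB, and adverse and serious adverse events go to an independent DSMB each year. Adverse events are themselves a safety endpoint, so a renal event recorded as one falls within it. This stands, and it defeats the inference that renal harm would go unreported. It does not supply a comparison by arm. The DSMB list contains no laboratory values, and the Section 9 adverse events come from a questionnaire, so a symptomless eGFR fall reaches either only if someone records it as an adverse event.

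A reader might also infer that the mixed model and the ANCOVA are the SAP's only methods. They are not: descriptive statistics and Fisher or chi-square tests are named, though linked to no renal variable. The mixed model uses all available data, so values from a subject removed later stay in it; the loss of removed subjects concerns the additional completer ANCOVA. Nor does the SAP say that eGFR enters a mean model, so dilution is conditional. The SAP also keeps the comprehensive metabolic profile, under which Section 5 lists creatinine and BUN.

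A further tempting inference is that low glucose would be scored as benefit, because glucose appears only in exploratory aim 7. The documents do not say this. Section 15 states that exenatide alone usually does not cause hypoglycaemia; insulin, meglitinides and sulfonylureas are excluded; and side effects are assessed weekly.

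Finally, safety is an exploratory aim in what Section 12 calls an initial test of efficacy, and the SAP specifies no safety analysis of any kind. Both points are true. They limit what the renal table can claim but are not reasons to omit it.

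**Conclusion.** The concern holds in limited form. A named and potentially serious risk is measured at five scheduled time points and has its own removal rule, yet no safety aim, safety endpoint or SAP analysis compares it between arms. A laboratory-only eGFR fall could therefore be absent from the between-arm results. That conclusion rests on the text alone.

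The size of the dilution rests on assumed inputs. Across falls of 30 to 40 ml/min and SDs of 10 to 20, two or three affected subjects of 35 move the arm mean by 1.7 to 3.4 ml/min, with 6 to 29% power, and this matters only if eGFR is analysed as a mean.

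The documents do not support the stronger readings that renal harm would go unreported, that it would necessarily be averaged away, or that low glucose would count as improvement. The change should be made because the risk is named and the samples are already scheduled, not because the trial could test for renal harm.

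**What to change.** Add eGFR and creatinine to the safety endpoints (protocol Sections 3 and 9) and to the SAP, as one descriptive table by arm in all subjects who received at least one injection. Use all scheduled, repeat and exit-visit values where available; Section 14 names a CBC and basic metabolic profile at the exit visit but not eGFR. Show:

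- the number with eGFR below each limit the protocol already states (35 and 30 ml/min);
- the number removed for eGFR;
- each subject's lowest value and largest fall from baseline.

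Give exact confidence intervals for the proportions. Do not restrict the table to completers. If it is added after unblinding, label it post hoc.

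Before counting removals, the sponsor should reconcile Section 13 with Sections 5 and 14, so that removal for eGFR has one definition. Which rule applies is a clinical decision outside this review.

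The cost is a few sentences in the SAP and one table, with no new samples, visits or staff. The intervals will be wide, and the text should say that an empty row is not evidence of renal safety.

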### **4) Background\***

Negative symptoms and cognitive deficits in schizophrenia: Schizophrenia can be a devastating illness for patients, often producing life-long disability. Two major factors contributing to

functional disability in schizophrenia are negative symptoms and cognitive impairment, which are the biggest obstacle to achieving an independent and productive lifestyle, with these deficits being refractory to current drug treatments.

(1-3).

**Inflammation and negative symptoms:** Evidence of immune dysfunction and inflammation has been described in patients with schizophrenia (4-7). A series of recent studies from our group have demonstrated abnormal patterns of immune activation, including elevated serum levels of IL-1 $\beta$ , IL-6, TNF- $\alpha$ , interferon- $\gamma$ , increased nuclear factor- $\kappa$ B (NF- $\kappa$ B) activation and its mRNA expression in peripheral blood mononuclear cells (PBMC) in first episode schizophrenia patients (8, 9). The findings from our group and others also support an altered immune function characterized by shifting from a Type 1 (cellular) to a Type 2 (humoral) immune response (10, 11). Several studies have suggested that the dysregulation of inflammatory and immunological processes is likely related to the manifestation of symptoms and treatment response of schizophrenia (12, 13). We reported that specific markers for inflammation, including elevated blood levels of C-reactive protein (CRP) and white blood cell count (WBC), are associated with negative symptoms of schizophrenia (14, 15).

**Inflammation and cognition:** Considerable evidence links inflammation to cognitive impairment in non-schizophrenia populations (16). Higher plasma levels of CRP and interleukin-6 (IL-6) have been associated with poorer cognitive performance at baseline and with a greater risk of cognitive decline over a 2-year follow-up period in well-functioning elders (17). In the community-based Framingham study cohort, higher levels of IL-1 and TNF- $\alpha$  both were markers of future risk of Alzheimer disease in older individuals (18). Further, it has been suggested that long-term use of non-steroidal anti-inflammatory drugs (NSAIDs) offers some protection against the development of Alzheimer's disease (19). Inflammation is also associated with cognitive impairment in schizophrenia. In a sample of 413 patients with schizophrenia, Dickerson et al. measured the levels of CRP, reported that those with CRP  $\geq$  5 mg/mL had significantly lower cognitive scores than those with CRP  $<$  5 mg/mL (20). We recently found that schizophrenia patients with a TNF- $\alpha$  -308G/G genotype (N=83) had better executive function than those with G/A or A/A genotypes (N=31).

**Hippocampal volume loss in schizophrenia:** Studies have found evidence for a progressive loss of cortical tissue volume in the early phase of schizophrenia. First episode patients have shown cortical volume reductions of 1% or more per year; these changes are thought to be most active during the first few years of the illness, with some leveling off of this degenerative process as the disease becomes chronic. Progressive volume loss seems most pronounced in the frontal and temporal gray matter areas (21). Reduced hippocampal volume has been consistently reported in both first episode psychosis and chronic schizophrenia (22-24). Postmortem studies in schizophrenia patients have also demonstrated subtle anomalies in limbic structures, most consistently in the hippocampus (25).

Hippocampal volume loss – in relation to cognitive deficits, negative symptoms and functional impairment in schizophrenia: The hippocampus is a highly plastic brain region; new neurons are continuously produced in the dentate gyrus of the hippocampus throughout life. The amount of neurogenesis correlates closely with the hippocampal function of learning and memory (26, 27). Hippocampal pathology has been proposed to underlie clinical, cognitive and functional impairments in schizophrenia (28). Progressive cortical loss is associated with more negative symptoms, cognitive decline and a more severe course of illness (21). A significant inverse correlation between left hippocampal volume and negative symptoms of schizophrenia has been reported previously (29). Studies also demonstrated a significant correlation between reduced hippocampal volume and cognitive deficits in patients with schizophrenia (30). Further, a recent study reported that bilateral hippocampal increase occurs in a minority of patients following their first psychotic episode and is associated with good outcome across clinical, cognitive and functional domains (31).

Inflammation and hippocampal volume loss in schizophrenia: Overwhelming evidence from animal studies indicates that activation of microglia and the subsequent release of pro-inflammatory cytokines including IL-1 $\beta$ , TNF- $\alpha$  and IL-6 have negative effect on hippocampal neurogenesis. Activated microglia and inflammatory cytokines may reduce cell proliferation, survival and function of new neurons in hippocampus (32). The initial work demonstrating that classically activated microglia impair hippocampal neurogenesis was reported by Monje et al. (33) and Ekdahl et al. (34) following lipopolysaccharide (LPS) administration in rats. Earlier post-mortem studies have shown the presence of microglial activation in the brains of patients with schizophrenia (35, 36). More recent studies using positron emission tomography (PET) in live patients with schizophrenia further demonstrated microglia activation especially in temporal-limbic gray matter (37, 38). Microglia, a major source of various inflammatory cytokines and free radicals such as superoxide and nitric oxide in the brain, play a crucial role in apoptosis and the neurodegenerative process (39). Negative symptoms and cognitive deficits in schizophrenia may in part be related to inflammation-induced reduction in adult hippocampal neurogenesis and volume loss.

Anti-inflammatory treatment and hippocampal neurogenesis: Administration of the microglia inhibitor, minocycline, blocked the LPS-induced decrease in new neuron survival in the hippocampus (34). In another study, inflammatory blockade with indomethacin, a common nonsteroid anti-inflammatory drug, restores hippocampal neurogenesis after LPS-induced inflammation in rats (33). Anti-inflammatory treatment may preserve hippocampal neurogenesis, therefore slow down or even reverse the hippocampal volume loss process in schizophrenia.

Anti-inflammatory treatment in schizophrenia: Muller et al. conducted a 6-week trial of celecoxib augmentation to amisulpride treatment in patients with first episode of schizophrenia, and found a significant therapeutic effect of celecoxib as measured by the PANSS total score and the negative symptom subscale score (40, 41). Another commonly used anti-inflammatory agent, aspirin, was also studied in the schizophrenia population. It was reported that aspirin as an adjuvant therapy to antipsychotic treatment reduced schizophrenia symptoms as measured by

the PANSS total score (42). A recent study also found minocycline, a second-generation tetracycline that exerts anti-inflammatory and antimicrobial effects, was associated with improvement in negative symptoms and executive function in early phase schizophrenia (43, 44). Despite the promise of potential benefit of celecoxib, aspirin and minocycline in schizophrenia treatment, there are both important scientific and safety issues to be addressed: Scientifically, it is unclear which brain target is engaged in anti-inflammatory treatment, and by which mechanism these anti-inflammatory drugs affect the target. On the safety aspect, the adverse side effects related to these drugs limit their potential clinical therapeutic utility in the schizophrenia population. Celecoxib and other COX-2 inhibitors have been associated with an elevated risk of cardiovascular disease (45), which is a serious comorbid medical condition in patients with schizophrenia. The cardio-protective non-selective COX inhibitor aspirin is arguably preferable. However, it is well established that aspirin, especially used in a relatively high dosage, is associated with a significant risk for GI bleeding. Tetracyclines are known to have side effects of pigmentation changes, pediatric tooth discoloration and photosensitivity reactions (46).

GLP-1 and its analogues: Glucagon-like peptide-1 (GLP-1) is an endogenous 30-amino acid peptide hormone, which is secreted from the intestinal L-cells in response to ingested carbohydrate and fat. It stimulates insulin secretion in a glucose-dependent manner and inhibits glucagon secretion from the pancreas. Exendin-4 is a peptide agonist of GLP-1 receptor (GLP-1R) that promotes insulin secretion. Two longer-lasting GLP-1 analogues (exenatide - a synthetic exendin-4, and liraglutide) are two FDA-approved medications for diabetes treatment. In addition to glycemic control, treatment with GLP-1 analogues is also associated with moderate weight loss, and improvement in cardiovascular risk factors (47). Given the overall favorable safety profile and weight effect, a low risk of hypoglycemia, and clinically meaningful improvements in HbA1c in various patient populations, the guidelines of the American Association of Clinical Endocrinologists (AACE) and the recently updated guidelines from the American Diabetes Association (ADA) assign exenatide and liraglutide a central role in the treatment of diabetes (48).

Exenatide, a synthetic exendin-4, is available in two formulations: twice daily and once weekly. Exenatide twice daily is the first glucagon-like peptide-1 (GLP-1) receptor agonist approved for the treatment of type 2 diabetes. Exenatide once weekly is the first glucose-lowering agent that is administered once per week. This long-acting formulation contains the same active ingredient as exenatide twice daily, except that the exenatide is encapsulated in dissolvable microspheres.

GLP-1 and inflammation: Recent evidence has shown that GLP-1 and analogues have anti-inflammatory activity. It has been shown that both activated microglia and activated astrocytes bind GLP-1 and that GLP-1 can prevent lipopolysaccharide (LPS)-induced increase in interleukin-1 $\beta$  (IL-1 $\beta$ ) in these cells (49). Other studies reported that exendin-4 can reduce monocyte adhesion to aortic endothelium in a model of atherosclerosis and prevent LPS-induced cytokine and chemokine mRNA synthesis in both human and mouse monocytes (50, 51).

Recent clinical studies also have demonstrated that exenatide exerts a potent anti-inflammatory effect (52-54). In a double-blinded, 16-week study with 23 patients with diabetes and inadequate glucose control, subjects were randomly assigned to receive exenatide (5 $\mu$ g twice daily for 4 weeks followed by 10 $\mu$ g twice daily for 12 weeks) or placebo; exenatide treatment significantly reduced oxidative stress and high sensitivity CRP (55). In a more recent study, 24 patients with diabetes were randomized to be on exenatide 10 $\mu$ g twice daily or placebo for 12 weeks; the results showed that exenatide significantly decreased reactive oxygen species generation, NF- $\kappa$ B binding, the mRNA expression of TNF and IL-1 $\beta$  in PBMC, and serum levels of IL-6 (56). In another study, patients with diabetes were treated with exenatide 2mg once weekly or 10 $\mu$ g twice daily for 30 weeks; in addition to improving glycemic control and lipids, both the once weekly and twice daily exenatide regimens significantly reduced serum levels of high sensitivity CRP (57).

GLP-1 and neuro-protection: GLP-1Rs are found in cerebral cortex, hippocampus, hypothalamus, and thalamus. The distribution of GLP-1 receptors (GLP-1Rs) in the brain suggests they may play an important role in the regulation of neuronal activity. In pre-clinical studies, GLP-1 and analogues protect motor activity, modulate long-term potentiation and synaptic plasticity, enhance neurogenesis, reduce apoptosis, protect neurons from oxidative stress, and reduce plaque formation in the brain in mouse models of Alzheimer disease, Parkinson disease, amyotrophic lateral sclerosis, stroke and other neurodegenerative diseases (58-60).

GLP-1 and longer-lasting analogues cross the blood-brain barrier (BBB) by simple diffusion, a property that is of great importance in order to be effective in the brain (61). In contrast, several neuro-protective growth factors such as nerve growth factor (NGF) and brain-derived neurotrophic factor (BDNF) do not cross the BBB, therefore have no effect in the brain if injected peripherally.

GLP-1 and hippocampus: Li et al. found that intraperitoneal treatment of exendin-4 in mice for 4 weeks increases cell proliferation and neuroblast differentiation in the adult mouse hippocampal dentate gyrus (62). Another study in mice demonstrated that intrahippocampal LPS injection induces cognitive decline via activation of NF- $\kappa$ B related inflammatory response; intraperitoneal treatment of exendin-4 reduces the inflammation and protects against cognitive impairment (63). A more recent study in mice reported that subcutaneous exendin-4 treatment presents traumatic brain injury induced changes in hippocampus gene expression and memory deficits (64). These studies demonstrated that peripheral administration of exendin-4 can inhibit inflammation and preserve neurogenesis in the hippocampus.

GLP-1 and cognition: In animal studies, treatment with GLP-1 analogues has been demonstrated to improve measures of cognitive function (65). For example, Mice injected daily for 8 weeks with GLP-1 exhibited significant improvement in recognition index on an object recognition test, indicating enhanced learning and memory (66). GLP-1R  $-\text{/-}$  knockout mice

demonstrate impaired spatial learning and memory as shown by their performance in the Morris water maze task, longer time to completion, and poorer recall of landmarks. They also performed poorly on an object recognition task, demonstrating inability to differentiate between familiar and novel objects (67).

**Summary of GLP-1:** Activation of the GLP-1R has shown neurotrophic, neuroprotective, and functional and behavioral benefit under numerous physiological and pathophysiological paradigms in pre-clinical studies. As GLP-1R stimulation has proven to be beneficial and well tolerated in diabetes treatment, it is reasonable to hypothesize that GLP-1 analogues including exenatide would likely be beneficial in human neurological or neuropsychiatric diseases. Several clinical trials are currently underway, testing GLP-1 analogues in mild cognitive impairment, Alzheimer disease and Parkinson disease ([www.clinicaltrials.gov](http://www.clinicaltrials.gov)). Based on the extensive evidence of its anti-inflammatory and neuro-protection effects, GLP-1 might be a potential novel treatment target for negative symptoms, cognitive deficits and metabolic problems in patients with schizophrenia. GLP-1 analogues show great promise as a novel treatment for schizophrenia.

